9.4.3. Secondary Endpoint(s)

Immunogenicity Endpoints

Descriptive statistics (geometric mean and confidence intervals, or median and interquartile range Q1-Q3, as appropriate) will be calculated for continuous immunologic parameters. Several definitions of serological response will be applied as applicable (GMC [S-ELISA]). Graphical representations of immunologic parameters will be made as applicable. Frequency tabulations will be calculated for discrete (qualitative) immunologic parameters, as applicable.

In addition, the ratio between neutralizing and binding antibodies as determined by S-ELISA and VNA, respectively, will be calculated together with confidence intervals. More details will be provided in the SAP.

The immunogenicity analyses will be performed on the PPI population. Immunogenicity analyses will also be done on the FAS (participants who became infected during the study will be analyzed as a subgroup and shown in the graphs using different colors and symbols).

Safety Endpoints

No formal statistical testing of safety data is planned. Safety data will be analyzed descriptively by vaccine group. In addition, for selected tables, tabulations pooled by vaccine dose will also be provided. All safety analyses will be made on the FAS.

Adverse Events

The verbatim terms used in the eCRF by investigators to identify AEs will be coded using the Medical Dictionary for Regulatory Activities (MedDRA). All reported AEs with onset during the active vaccination phase (ie, AEs occurring after vaccination up to 28 days post vaccination), and all SAEs/MAAEs/AESIs will be included in the analysis. (S)AEs caused by molecularly confirmed SARS-CoV-2 infection will be removed at the analysis level from the (S)AE listings and tables and presented separately. For each AE, the percentage of participants who experience at least 1 occurrence of the given event will be summarized by vaccine group.

Summaries, listings, datasets, or participant narratives may be provided, as appropriate, for those participants who die, who discontinue intervention due to an AE, or who experience a severe AE, an AESI, or an SAE.

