4. POPULATIONS (ANALYSIS SETS) FOR ANALYSIS

For vaccine studies, study intervention assignment will follow the as treated principle: all analyses (including safety, immunogenicity) will be analyzed by the received vaccine.

Analysis Sets	Description
All screened participants (ALL)	The “all screened participants” set includes all participants that were screened, regardless of whether they were enrolled and/or randomized.
All randomized participants (ALL RANDOMIZED)	The “all randomized participants” set includes all participants that were randomized to one of the treatment groups.
Full Analyses Set (FAS)	The Full Analysis Set will include all participants with at least one vaccine administration documented
Per Protocol Immunogenicity Set (PPI)	The Per Protocol Immunogenicity population will include all randomized and vaccinated participants for whom immunogenicity data are available excluding participants with major protocol deviations expected to impact the immunogenicity outcomes (see section 4.1). In addition, samples obtained after missed vaccinations or samples obtained from participants after SARS-CoV-2 infection occurring after screening (if applicable) will be excluded from the analysis set (see below section 4.1).
NI Analysis Set	The NI analysis set will include all PPI participants who are SARS-CoV-2 seronegative at study entry ^a .

^a SARS-CoV-2 seronegative as assessed by central testing (based on S- and/or N- serology at baseline)

NB. As detailed in Section 4, formal non-inferiority hypothesis testing will be performed on either the NI set or on the PPI set under different scenarios (Scenario 1 or Scenario 2, respectively).

Further details on the selection of PPI and NI set are described below.

The safety and reactogenicity analyses will be censored at the date of unblinding or the receipt of an unscheduled vaccine, whichever event occurs first. AEs reported after unblinding or receipt of an unscheduled vaccine, whichever comes first, will be listed.

The immunogenicity analyses will be censored at the date of the receipt of an unscheduled vaccine. Immunogenicity samples taken after the receipt of an unscheduled vaccine will be included in the listings and flagged.

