4.1. Selection of PPI dataset

- Samples obtained from participants after SARS-CoV-2 infection occurring after screening (if applicable) will be excluded from the analysis set.
 - This includes COVID-19 cases with a positive RT-PCR or molecular test, but also participants who develop a post-baseline positive result in non-S-based serology (e.g. N-ELISA or equivalent assay, such as the Roche Elecsys anti-SARS-CoV-2 assay) if the test was negative at baseline. Samples at the time of positive RT-PCR or molecular test, or non-S-based serology and thereafter will be excluded from PPI.
 - Participants with missing or having undetermined SARS-CoV-2 serostatus at baseline will be excluded from PPI.
- Major Protocol Deviations (MPDs) with impact on immunogenicity will be considered for the PPI population. MPDs are defined in the MPD Criteria document. Different rules are applicable for selected MPDs with impact on immunogenicity:
 - For MPDs with impact on immunogenicity which concern inclusion or exclusion criteria (category: entered but did not satisfy criteria), the whole subject will be excluded from PPI.
 - For MPDs with impact on immunogenicity which can affect immunogenicity outcomes from the time of PD and thereafter, such as missed vaccinations, out of window vaccinations (Day 57 visit), use of disallowed concomitant medications or off-study COVID-19 vaccines (categories: received a disallowed concomitant treatment, received wrong treatment or incorrect dose, developed withdrawal criteria but no withdrawn, in addition to ‘missed vaccination’ under the category ‘Other’, and ‘received vaccination outside of visit window’ under the category ‘Dosage & Administration’), any samples obtained at the time of PD and thereafter will be excluded from PPI. Samples taken from the subject prior to such PDs can be included in PPI.
 - For MPDs with impact on immunogenicity which can affect immunogenicity outcomes only at the time of PD, such as out of window visits or blood collections (category: Other except for missed vaccination or out of window vaccinations which is included in the rule above), samples obtained at the time of PD will be excluded from PPI only. Samples taken from the subject prior to or after such PDs can be included in PPI.
 - The exact PD rules may be amended, or other PD types may be added, this will be further described in the DPS. For PDs relating to out of window visits or sampling, the windows will be defined as indicated in Section 5.1.3.

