5.1.5. Definition of Subgroups

The following subgroups will be investigated for immunogenicity: Sex, Age group, SARS-CoV-2 Serostatus at baseline and race. For selected safety and immunogenicity assessments, subgroup analysis will include age group, serostatus and BMI. Sub-group analysis for serostatus at baseline will only be done if at least ~10% of participants are seropositive at baseline. Final analysis for immunogenicity may include subgroups analyses for SARS-CoV-2 infection during the study and for off-study COVID-19 vaccination.

Subgroup	Definition
BMI	
 underweight $<18.5 \text{ kg/m}^2$ normal $18.5-25 \text{ kg/m}^2$ overweight $25-30 \text{ kg/m}^2$ obese $\geq 30 \text{ kg/m}^2$
Age Group 1	
 18-40 41-55
Age Group 2	
 18-25 26-40 41-55
Ethnicity	
 Hispanic or Latino, Not Hispanic or Latino, Not Reported Unknown
Sex	
 Male Female Intersex Unknown
Race ^a	
 American Indian or Alaska Native Asian Black or African American

Subgroup	Definition
	
 Native Hawaiian or other Pacific Islander White Not reported Unknown
SARS-CoV-2 Serostatus ^b at baseline	
 Positive Negative Missing
SARS-CoV-2 infection ^c during study	
 Yes No
Off-study COVID-19 vaccination during the study	
 Yes No

^aIf multiple race categories are indicated, the Race is recorded as 'Multiple'

^bSerostatus at baseline will be based on central testing, namely S and/or non-Spike-based serology (e.g. N-ELISA or equivalent assay, such as the Roche Elecsys anti-SARS-CoV-2 assay), as available, and is defined as:

- Positive for participants who are positive at baseline by S-ELISA, and/or non-S-based serology (e.g. N-ELISA or equivalent assay, such as the Roche Elecsys anti-SARS-CoV-2 assay), as available.
- Negative for participants who are negative at baseline by S-ELISA, and non-S-based serology (e.g. N-ELISA or equivalent assay, such as the Roche Elecsys anti-SARS-CoV-2 assay), if available.
- Missing if data on all of the above assays are missing, or if one of the assays is missing and the other is negative.

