5.4. Immunogenicity

5.4.1. General Considerations

Immunogenicity results will be presented by vaccine group and per scheduled time point as appropriate using visit windows (see Section 5.1.3).

For the PPI analysis samples taken outside of the allowed window as described in section 5.1.3 will be excluded from the table and graphs (but will be included in the listing and clearly marked as results not included in the PPI analyses). For the FAS analysis, samples taken outside of the allowed windows will be included in the tables and graphs.

Listings will be presented by vaccine group and per phase and analysis time point.

Key immunogenicity subgroup analyses will also be performed by BMI, ethnicity, race, sex, participants who were infected with SARS-CoV-2 during the study or those that received an alternative vaccine. Categorical variables will be summarized with a frequency table showing counts and percentages. This will be done for both the main study and sub study separately. Continuous variables will be summarized using the following statistics, as appropriate:

number of observations, geometric mean, arithmetic mean (mean), 95% confidence interval (CI) for the mean, standard deviation (SD), standard error (SE), median, quartiles (Q1 and Q3), minimum and maximum. This will be done for both main study and sub study separately.

Data listings, subject profiles and/or subject narratives may be provided as appropriate. This will be done for both main study and sub study separately.

Binary variables will be summarized using the following statistics: number of observations, percentages and Exact Clopper-Pearson 95% confidence interval (CI). This will be done for both main study and sub study separately.

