5.5.3. Analysis Methods

Formal non-inferiority hypothesis testing will be performed on either the NI set (Scenario 1) or on the PPI set (Scenario 2) as described in Section 4.

Descriptive non-inferiority and additional immunogenicity assessments may be performed on other populations and subgroups (e.g., PPI, or on participants in the PPI who are SARS-CoV-2 seropositive at baseline, etc.).

Immunogenicity analyses may also be done on the FAS (participants who became infected during the study will be analyzed as a subgroup and will be shown in the graphs using different colors

and symbols). Samples taken outside of the allowed windows as described in section 5.1.3 (included in the FAS analysis and excluded from the output in the analysis on PPI) will be included and flagged in the listings as results not included in the PPI analyses.

Key immunogenicity subgroup analyses will also be performed by age group, sex, BMI, race, ethnicity, and serostatus at baseline, as defined in Section 5.1.5.

Categorical variables will be summarized with a frequency table showing counts and percentages.

Continuous variables will be summarized using the following statistics, as appropriate: number of observations, geometric mean, arithmetic mean (mean), 95% confidence interval (CI) for the mean, standard deviation (SD), standard error (SE), median, quartiles (Q1 and Q3), minimum and maximum.

Data listings, participant profiles and/or participant narratives may be provided as appropriate.

Binary variables will be summarized using the following statistics: number of observations, percentages, and Exact Clopper-Pearson 95% CIs.

Formal NI testing will be applied to demonstrate NI of 1-dose and 2-doses of 9×10^{10} vp, 7×10^{10} vp, 3.5×10^{10} vp, 2.5×10^{10} vp and 1.25×10^{10} vp Ad26.COV2.S versus 1-dose and 2-doses of 5×10^{10} vp Ad26.COV2.S (release titer), using a NI margin of 2/3 for the GMC ratios.

The following 2 sets of hypotheses (1 dose and 2 doses) will independently be tested sequentially:

Post-dose 1

1a) NI after 1-dose of Ad26.COV2.S 9×10^{10} vp versus 1-dose of Ad26.COV2.S 5×10^{10} vp (release titer)

1b) NI after 1-dose of Ad26.COV2.S 2.5×10^{10} vp versus 1-dose of Ad26.COV2.S 5×10^{10} vp (release titer)

1c) NI after 1-dose of Ad26.COV2.S 7×10^{10} vp versus 1-dose of Ad26.COV2.S 5×10^{10} vp (release titer)

1d) NI after 1-dose of Ad26.COV2.S 3.5×10^{10} vp versus 1-dose of Ad26.COV2.S 5×10^{10} vp (release titer)

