6. OTHER ANALYSES

6.1. Immunogenicity Analyses

Immunogenicity analyses will use the PPI and/or NI set (as applicable). Where relevant, immunogenicity analyses will include SARS-CoV-2 serostatus at baseline as a subgroup. Immunogenicity analyses will also be done on the FAS (participants who became infected during

the study will be analyzed as a subgroup and shown in the graphs using different colors and symbols). Data will be analyzed by vaccine group.

Key immunogenicity assay results will also be analyzed for the subgroups defined in Section 5.2.1.

Data will be presented by scheduled time point. For the PPI analysis, samples taken outside of the allowed window as described in section 5.1.3 will be excluded from the tables and graphs (but will be included in the listings and clearly marked as results not included in the PPI analyses). For the FAS analysis, samples taken outside of the allowed window will be included.

Note: analyses that are potentially unblinding at the individual participant level (e.g. graphs showing individual data tied to COVID-19 infection status, especially when the number of COVID-19 infections is low and/or when time of infection is indicated) will be carried out after official unblinding of the trial, or will be carried out exclusively on specific groups (or other clearly defined subgroups) after these are unblinded. Alternatively, prior to unblinding, these analyses can be performed in a completely blinded manner (e.g. tables with only a single column pooling all regimens).

The following exploratory analysis will be performed on the sub-study for descriptive purposes:

- Transcriptomics: The relative quantity of transcripts (as measured by mRNA sequencing) in whole blood following vaccination will be measured. The magnitude and type of differentially expressed genes relative to baseline and their kinetics will be compared post dose 1 and post dose 2, and between dose levels. Details are described in separate a study plan and Omics Statistical Analysis Plan.
- Proteomics: The relative abundance of serum proteins following the first and second dose of different Ad26.COV2.S dose levels will be measured relative to baseline and compared between dose levels. Details are described in a separate study plan and Omics Statistical Analysis Plan.

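### On the FAS, one whole-study infection flag mixes samples from before and after infection at Days 29, 57 and 71, and the SAP's censoring at an unscheduled vaccine conflicts with its planned off-study-vaccination subgroup

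*SAP*

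**What the plan says.** SAP 5.1.5 lists infection during the study and off-study COVID-19 vaccination during the study as subgroups, each with the levels Yes and No. Infection is a positive PCR, or conversion from negative at baseline to positive afterwards on a non-spike serology test. On timing of use, 5.1.5 says: "Final analysis for immunogenicity may include subgroups analyses for SARS-CoV-2 infection during the study and for off-study COVID-19 vaccination". SAP 5.4.1 is firmer: key subgroup analyses will be done for "participants who were infected with SARS-CoV-2 during the study or those that received an alternative vaccine". It also sets the display unit: "Immunogenicity results will be presented by vaccine group and per scheduled time point as appropriate using visit windows".

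The infected subgroup is placed on the FAS. Protocol 9.4.3 says that "participants who became infected during the study will be analyzed as a subgroup and shown in the graphs using different colors and symbols"; SAP 5.5.3 and 6.1 repeat this.

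The PPI works differently. SAP 4.1 states: "Samples at the time of positive RT-PCR or molecular test, or non-S-based serology and thereafter will be excluded from PPI".

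For other vaccines, SAP section 4 states: "The immunogenicity analyses will be censored at the date of the receipt of an unscheduled vaccine". It adds that later samples go to the listings, flagged. The sentence is not limited to one analysis set.

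**The concern.** Infection and off-study vaccination occur at different times in different people. A flag covering the whole study, crossed with a visit, sorts an early sample by something that may happen only later. A mean for infected participants at Day 29 would then be partly a mean of people not yet infected.

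Both documents have an exploratory objective on the immune response in vaccinated people with prior or breakthrough infection, and this table is the natural summary for it. The off-study-vaccination table has a different problem: one SAP sentence plans the subgroup, while another removes the samples that would make it informative.

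**Working it through.** The plan states no figure for this point, so the check is mainly a reading of the rules together.

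**Infected subgroup, by set and visit**

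| Set and visit | Content of the Yes group under the stated rules |
|---|---|
| FAS, Day 1 | All before the event, because infection is defined by a test after baseline |
| FAS, Days 29, 57, 71 | People already infected together with people infected later |
| FAS, Week 32 | Essentially all post-infection; the exception is anyone followed beyond Week 32 and infected after it |
| PPI, any visit | Only samples before the first positive test |

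No rule in SAP 5.1.5, 5.4.1, 5.5.3 or 6.1 assigns a sample to before or after the event. The colours and symbols in the graphs mark the participant, not the sample.

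**Off-study-vaccination subgroup**

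Sections 5.1.5 and 5.4.1 plan it. Section 4 ends the immunogenicity analyses at the unscheduled vaccine. Taken together, the summary tables for Yes contain no post-vaccine samples; these appear only in listings. The SAP does not define an unscheduled vaccine, but 4.1 removes PPI samples from the time of an off-study COVID-19 vaccine, which points the same way. Protocol 6.3 says data from the point of unblinding, including unblinding to obtain an authorised vaccine, will be analysed separately as described in the SAP. The SAP describes no such immunogenicity summary.

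**Scale at Day 29 (illustration only)**

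- From SAP sections 3 and 4.2: 27% of main-study participants were N-positive at Day 29 and 38% at Day 71.
- Assumption: b percentage points were already N-positive at baseline by central testing. The documents do not give b.
- Assumption: those positive at Day 29 are a subset of those positive at Day 71.
- Share of those converted by Day 71 who had not converted by Day 29 = 1 − (27 − b)/(38 − b) = 11/(38 − b).

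| b | Share not yet converted at Day 29 |
|---|---|
| 0 | 11/38 = 29% |
| 10 | 11/28 = 39% |
| 20 | 11/18 = 61% |

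If infection multiplied S-ELISA concentration by F, and the not-yet-infected started from the same level, the Day 29 GMC of the subgroup would be raised by F^(1 − share). For an assumed F of 5 this is 5^(27/38) = 3.1 at b = 0 and 5^(7/18) = 1.9 at b = 20. For an assumed F of 10 it is 5.1 and 2.5. Infections after Day 71 would increase the not-yet-infected share at all three intermediate visits.

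**The case against.** The strongest reply is that the problem is narrower than it looks, and much of that reply stands.

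- A reader might infer that the infected table never shows the response to infection. The documents do not support this: on the FAS, post-infection samples are kept, Day 1 is a proper baseline, and by Week 32 the group is essentially all post-infection.
- The table is not the only display. SAP 6.1.4 plans participant profiles over time and individual dot plots, and 6.1 foresees graphs in which the time of infection is indicated. These partly serve the objective, but the visit-wise GMCs at Days 29, 57 and 71 remain mixed.
- A reader might infer that the off-study-vaccination table is bound to show no vaccine effect. That requires the general censoring sentence to override the specifically planned subgroup. The planned subgroup could equally be read as an exception. What stands is a conflict between two SAP sentences. No stated objective asks for the response to an off-study vaccine, and protocol 6.6 places boosters after the last study visit, so the post-vaccine samples may be few.
- The SAP leaves mock-ups, programming instructions and some updated rules to the Data Presentation Specifications, which were not available. A dating rule could be there, but the SAP's own censoring sentence would still need reconciling.
- SAP 5.1.5 says these subgroups may be included at final analysis. SAP 5.4.1 says they will be performed.

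**Conclusion.** The point holds within limits. On the FAS, the infected subgroup's GMC mixes samples from before and after infection at Days 29, 57 and 71. On the PPI, the same subgroup would contain only samples from before the first evidence of infection. Section 4 and sections 5.1.5 and 5.4.1 conflict on off-study vaccination; read literally, that table has no post-vaccine samples.

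The size of the dilution cannot be estimated from the documents. The 29% to 61% rests on an assumed baseline share of 0 to 20 points. The SAP itself attributes the 27% and 38% to infection during the study, insensitive local tests, or both. A reader might take the 1.9- to 5.1-fold results as a prediction for this trial, but the rise after infection is also assumed, so they show direction only.

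A reader might also infer that the primary conclusion is at risk. It is not: these analyses are descriptive, and the non-inferiority analysis does not use these flags.

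**What to change.** For these descriptive FAS tables, define the classification in SAP 5.1.5 at sample level, using recorded dates:

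- (a) before any infection or off-study COVID-19 vaccine;
- (b) at or after first evidence of infection, using the trigger already in 4.1, with no prior off-study vaccine;
- (c) after an off-study vaccine, with no prior evidence of infection;
- (d) after both.

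Keep the participant profiles for within-person trajectories. In section 4, state that censoring at an unscheduled vaccine applies to the PPI and NI sets and to the main FAS summaries, but not to the tables for (c) and (d).

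The cost is SAP wording and a time-dependent flag. The PPI already needs date-based sample exclusion, and the protocol has positive SARS-CoV-2 results and the dates of other COVID-19 vaccines recorded, so no new data are required. The downsides are smaller cells, group membership that changes by visit, and N-conversion dated only to a sampling interval. Central N-serology is scheduled at Days 29 and 71 but not Day 57, so a Day 57 sample between a negative and a positive result is placed by convention unless the stored serum is tested.

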5.5. Primary Humoral Immune Response Endpoints

5.5.1. Definition of Endpoint(s)

S-ELISA will be used as a primary immunogenicity endpoint, for formal NI testing, to demonstrate non-inferiority for each of the hypothesis tests between the groups as stated in Section 2. This analysis will be based on:

Binding antibody concentrations to SARS-CoV-2 S protein as measured by ELISA 28 days after vaccination 1.

Binding antibody concentrations to SARS-CoV-2 S protein as measured by ELISA 14 days after vaccination 2.

GMCs derivations will be based on the Log transformed (\log_{10} scale) immune response (ELISA concentrations) 28 days post-dose 1- and 14-day post-dose 2 data.

NI of the statistical hypotheses (Section 1.3) will be demonstrated in terms of humoral immune response expressed by the GMCs of ELISA, using an NI margin of 2/3.

